2.3. Data Handling

2.3.1. Measurement Times

2.3.1.1. Visit Windows

Visit windows will not be used. The visit time point entered on the case report forms will be used. Unscheduled assessments, if any, will be listed, but will not be included in tabulations by visit.

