However, if 0 of 3 or ≤ 1 of 6 subjects treated at Dose Level 4 experiences DLT by Day 28, dose escalation will proceed to the next dose cohort, 320 mg/m² administered as an IV infusion over 2 hours twice weekly (Dose Level 5), on Days 1, 4, 8, 11, 15, 18, 22 and 25 of a 28-day schedule. A minimum of 3 subjects will be treated at this dose level. If 1 of 3 subjects treated at Dose Level 5 experiences DLT during Cycle 1, the cohort will be expanded to 6 subjects. If there are ≤ 1 of 6 subjects with DLT at Dose Level 5, this dose (320 mg/m² twice weekly) will be declared the MTD and RP2D. If, however, ≥ 2 of 6 subjects experiences DLT, then either 320 mg/m² weekly (Dose Level 2) or 240 mg/m² twice weekly (Dose Level 4) will be declared the MTD and RP2D based on additional factors (e.g., PK and PD parameters).

Dose-limiting toxicity will be defined as any one of the following events: prolonged myelosuppression (as defined by the National Cancer Institute [NCI] criteria specific for leukemia, i.e., marrow cellularity $< 5\%$ at ≥ 6 weeks from start of therapy without evidence of leukemia); \geq Grade 3 non-hematologic toxicity (excluding Grade 3 nausea, vomiting or diarrhea that is adequately controlled with supportive care and resolves to \leq Grade 2 within 48 hours, or Grade 3 electrolyte disturbances responsive to correction within 24 hours); \geq

Grade 3 liver function tests (LFTs) lasting > 7 days; treatment interruption > 14 days due to toxicity; or other important medical event.

Phase 2a (Expansion):

Subjects will be enrolled into the Phase 2 Expansion portion in three cohorts. Subjects will receive E6201 weekly or bi-weekly on a 28-day schedule, with the schedule and dose level established in the safety run-in portion of the study.

As of July 17, 2017, this study was terminated due to lack of sufficient efficacy in the Phase 1 dose escalation portion of the study. Therefore, the SAP will include patient listing data and dose cohort summary tables for the 28 patients enrolled in the study.

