3.4.2. Adverse Events

All AEs will be coded based on the Medical Dictionary for Regulatory Affairs (MedDRA; Version 17.0 or higher). An AE will be considered a treatment emergent adverse event (TEAE) if the onset is after the first dose of study drug or if the condition was present at baseline but worsened after the first dose. All other AEs will be considered preexisting events.

All AEs for each subject will be listed, including Treatment Emergent status, intensity grading, relationship to study drug, action taken and outcome. Subject listings of deaths, serious TEAEs, and TEAEs leading to treatment discontinuation will be presented.

TEAE summaries will be produced for each dose cohort for subjects in FAS population. All TEAE summaries will show the number and percentage of subjects experiencing at least 1 TEAE for each preferred term, arranged by system organ class, and the number of unique occurrences of the event. Separate summaries will be produced by relationship to study medication and by severity. Subjects with multiple events will be counted only once per SOC

and preferred term. For each level of summarization, the event with the highest level of severity, grade, or strongest drug relationship will be presented. TEAEs with Grade 3 or Grade 4 and drug-related TEAEs with Grade 3 or Grade 4 will be summarized. TEAEs leading to study drug interruption or discontinuation, and Serious TEAEs will be provided in separate listings.

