3.4.3. Clinical Laboratory Results

Laboratory data will be listed for each subject using FAS population. Laboratory values will be graded according to the NCI-CTCAE version 4.03 criteria. Laboratory results will be summarized by dose cohort using number of non-missing observations, mean, standard deviation, median, minimum, and maximum.

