4.1.3.3. Laboratory Assessments

- Hematology Laboratory Results by Visit
- Chemistry Laboratory Results by Visit

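### Laboratory values are CTCAE-graded, but no laboratory table uses the grades, and the by-visit tables leave out unscheduled draws

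*SAP*

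**What the plan says.** Section 3.4.3 says "Laboratory values will be graded according to the NCI-CTCAE version 4.03 criteria". It then fixes the summary: "Laboratory results will be summarized by dose cohort using number of non-missing observations, mean, standard deviation, median, minimum, and maximum". Section 4.1.3.3 names two laboratory tables, "Hematology Laboratory Results by Visit" and "Chemistry Laboratory Results by Visit", and section 4.1 presents all tables by dose cohort. Section 2.3.1.1 adds that "Unscheduled assessments, if any, will be listed, but will not be included in tabulations by visit".

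Three other provisions bear on the point. Section 3.4.3 also states that "Laboratory data will be listed for each subject using FAS population". Section 3.4.2 plans that "TEAEs with Grade 3 or Grade 4 and drug-related TEAEs with Grade 3 or Grade 4 will be summarized", and section 4.1.3.2 lists TEAE tables by severity and for Grades 3 and 4. Section 1.3.2 includes among the DLT criteria liver tests at or above this level and duration: "Grade 3 liver function tests (LFTs) lasting > 7 days".

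**The concern.** The SAP assigns a toxicity grade to each laboratory value and then plans no table that counts the grades. Both laboratory tables are by visit, so the rule on unscheduled assessments keeps those values out of both.

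Safety and tolerability are the Phase 1 primary objective (section 1.2.1). After termination the SAP is confined to listings and dose-cohort summaries for 28 patients (section 1.3.2), and no primary or secondary endpoint analysis will be given (sections 3.3.1 and 3.3.2). The safety tables are therefore the main statistical output. Section 1.1 names laboratory parameters as a safety assessment beside adverse events, and the DLT definition judges liver tests by grade. A reader comparing dose cohorts would want the number of subjects who reached Grade 3 or 4 on treatment, and the laboratory tables do not give it.

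**Working it through.** The SAP states no figure to reproduce. The check is to follow a laboratory value through the planned outputs.

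**1. What a cell of a laboratory table holds.** For one visit and one dose cohort it holds the count of non-missing values, mean, SD, median, minimum and maximum. Extremes at scheduled visits are therefore visible, but grade counts are not. In a cohort of 3 with complete data, the minimum, median and maximum are the three values themselves, so a careful reader could grade that visit. In a cohort of 6, five summaries (mean, SD, median, minimum, maximum) do not in general fix six values. In neither case can the reader tell whether the extreme at one visit and the extreme at the next belong to the same subject. The number of subjects who ever reached Grade 3 or 4 cannot be recovered.

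**2. Baseline.** Section 2.3.1.2 defines a baseline value, but section 3.4.3 plans neither change nor grade shift from it. An abnormality present at entry and one that arose on treatment look alike in the tables.

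**3. Where one subject's Grade 3 value appears.**

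| Draw | Reported as an AE? | Laboratory tables | TEAE severity and Grade 3/4 tables | Listings |
|---|---|---|---|---|
| Scheduled | Yes | In the descriptive statistics, not as a grade | Yes, if treatment-emergent | Yes |
| Scheduled | No | In the descriptive statistics, not as a grade | No | Yes |
| Unscheduled | Yes | No | Yes, if treatment-emergent | Yes |
| Unscheduled | No | No | No | Yes |

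Only the last row is missing from every summary table. Rows 3 and 4 are missing from the laboratory tables, and no row is counted by grade there.

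**4. Size of one case.** Section 2.1 plans 3 to 6 subjects per dose cohort. For one subject whose Grade 3 value was seen only at an unscheduled draw:

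- cohort of 6: 1/6 = 16.7% in truth, 0/6 = 0% in the laboratory tables;
- cohort of 3: 1/3 = 33.3% in truth, 0/3 = 0% in the laboratory tables.

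These figures concern the laboratory tables only. If the event was also reported as a TEAE, the Grade 3/4 TEAE table shows the subject. Replacement under section 1.4.4 could make a treated cohort larger than 6 and the share smaller.

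**The case against.** The strongest reply has four parts.

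*Unscheduled values belong to no nominal visit, so leaving them out of by-visit tables is normal.* This stands. The rule in section 2.3.1.1 is not an error, and the fix keeps it. The gap is that no other laboratory table complements it.

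*Graded toxicity is already covered by the adverse event tables.* This stands in part. A reader might infer that the worst laboratory toxicities appear in no summary table. The SAP does not support that: the TEAE severity and Grade 3/4 tables are not restricted by visit, so a laboratory toxicity reported as an AE enters them whichever draw found it. Which abnormalities must be reported as AEs is commonly a protocol matter, and its absence from the SAP is no fault. But the coverage then depends on AE reporting, and a table built from the graded values would check it independently.

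*The extremes are shown and everything is listed.* This also stands in part. It would be wrong to say that laboratory data are reduced to means, since the minimum and maximum are tabulated at each scheduled visit. Every value can be found in the listings. A count of subjects by worst grade would still have to be made by hand.

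*Nothing depends on these tables.* The study has stopped, no hypothesis test is planned (section 2.4.2), and the safety committee reviewed each cohort on an ongoing basis (section 1.1). That limits the consequence to how clearly the final safety results are reported. It does not remove it, because those results are what the SAP now exists to deliver.

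**Conclusion.** The point holds as a cheap and useful improvement. The laboratory tables cannot show how many subjects per dose cohort reached Grade 3 or 4 or worsened from baseline, and a peak found only at an unscheduled draw is absent from them. One such subject is 17% of a cohort of 6 or 33% of a cohort of 3, against 0% in the laboratory tables.

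This rests on the table list in section 4.1 being complete and on cohorts of the planned size. The SAP does not say how often unscheduled draws were taken or why. That they tend to follow an abnormal value is an assumption, so no frequency or direction of understatement can be claimed for this trial.

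A reader might also infer that the plan would hide liver-test DLTs. The document does not support that. The criterion requires Grade 3 or higher for more than 7 days, and nothing in the SAP says that DLTs are derived from these end-of-study tables. Duration has to be read from dated values in the listings, and a worst-grade table would not show it either.

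**What to change.** Keep the by-visit tables on scheduled values. Add to sections 3.4.3 and 4.1.3.3 a table, by dose cohort in the FAS, of each subject's worst post-baseline CTCAE grade with shift from baseline grade, for hematology and for chemistry. State in both sections that scheduled and unscheduled values count towards the worst grade, and use the baseline already defined in section 2.3.1.2. Note under the table that it does not identify liver-test DLTs, because it carries no duration.

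The cost is one or two extra tables. The values are already to be collected and graded, so no new data are needed.

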2.3.1.2. Baseline Values

The screening assessments are performed within 28 days of Cycle 1, Day 1, before the first dose of study medication. Unless otherwise mentioned, baseline will be the last observation before patients receive initially assigned dose. Generally, this will be Cycle 1 Day 1 pre-dose measurements. If a pre-dose assessment is not performed on Cycle 1 Day 1, the immediate previous non-missing value, including screening, will be treated as baseline. If there are multiple baseline assessments, the most recent one will be flagged as the baseline value and will be used for statistical analysis (evaluations may occur on the same day as Study Day 1, prior to dosing).

2.3.2. Missing Data Conventions

Unless otherwise specified, missing data will be considered missing and will not be imputed.

2.3.3. Imputation of Incomplete Dates

Imputation of partial dates may be performed during the data analysis and will be documented. For start date of Adverse Event (AE) or Concomitant Medication (CM) with a missing day, the imputed date is the first day of the month. For stop date of AE or CM with a missing day, the imputed date is the last day of the month. For start date with both missing day and missing month, the imputed date is the subject start study date if AE or CM start year is the same as study start year. Otherwise, the imputed start date is the first day of the year. For stop date with both missing day and missing month, the imputed date is the subject end of study date if AE or CM stop year is the same as the study end year. Otherwise, the imputed stop date is the last day of the year.

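### An AE with a missing onset day is dated to the 1st of the month with no check against first dose, so new post-dose events can drop out of the TEAE tables

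*SAP*

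**What the plan says.** Section 2.3.2 sets the default that "missing data will be considered missing and will not be imputed" unless otherwise specified. Section 2.3.3 then allows an exception for dates: "Imputation of partial dates may be performed during the data analysis and will be documented". For an AE or concomitant-medication start date "with a missing day, the imputed date is the first day of the month". When the month is missing as well, "the imputed date is the subject start study date if AE or CM start year is the same as study start year"; otherwise 1 January of that year is used.

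Section 3.4.2 makes an AE treatment-emergent "if the onset is after the first dose of study drug", or if it was present at baseline and worsened after first dose. It adds: "All other AEs will be considered preexisting events".

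Section 4.1.3.2 names seven AE tables, two of them for serious events. All seven are restricted to TEAEs and are shown by dose cohort. Section 3.4.2 also promises a wider listing: "All AEs for each subject will be listed, including Treatment Emergent status".

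**The concern.** The missing-day rule and the TEAE definition do not fit together. The imputed onset is never later than the true onset, so imputation can turn a post-dose event into a pre-dose one but never the reverse. For a safety summary that is the anti-conservative direction.

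The rules are also uneven. A date with only the year known can be anchored to the subject's start in the study, while a date with month and year known has no anchor. The start date used for that anchor is not defined in the SAP. That is a term to define, not a demonstrated error.

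The study was terminated in Phase 1, and sections 3.3.1 and 3.3.2 drop the primary and secondary efficacy analyses. The dose-cohort safety tables for 28 patients are therefore a central output of the report.

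**Working it through.** **1. The rules on one case.** First dose 14 June, true onset 20 June, day not recorded. Section 2.3.3 gives 1 June. That is before 14 June, so under section 3.4.2 a new event is pre-existing and is in no TEAE table.

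**2. All cases within one month.** A 30-day month has 30 × 29 / 2 = 435 pairs of first-dose day and later onset day. In 29 of them dosing is on the 1st, so the imputed date ties with first dose. In the other 435 − 29 = 406 (93.3%) the imputed date falls before first dose. None falls after it. If a tie does not count as after, all 435 are lost.

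**3. Allowing for onsets in later months.** The SAP gives no onset distribution. I assume first-dose dates uniform over a 4-year calendar cycle (1,461 dates; 48 months: 28 of 31 days, 16 of 30, three of 28, one of 29) and onset days uniform in a window of 1 to W days after first dose. An onset in a later month is imputed to a date after first dose and is classed correctly. An onset in the same month ties if dosing was on the 1st and is otherwise placed before first dose.

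For W = 28:
- Date pairs: 1,461 × 28 = 40,908.
- Same-month pairs per month: 462 (31 days: 465 less 3 with a gap above 28 days), 434 (30 days: 435 less 1), 406 (29 days), 378 (28 days).
- Same-month total: 28 × 462 + 16 × 434 + 406 + 3 × 378 = 21,420.
- Ties: 45 × 28 + 3 × 27 = 1,341.
- Before first dose: 21,420 − 1,341 = 20,079.
- After first dose: 40,908 − 21,420 = 19,488.

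The same count for other windows gives:

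| True onset after first dose | Pairs | Imputed before dose | Tie | Imputed after dose |
|---|---|---|---|---|
| 1–7 days | 10,227 | 8,547 (83.6%) | 336 (3.3%) | 1,344 (13.1%) |
| 1–28 days | 40,908 | 20,079 (49.1%) | 1,341 (3.3%) | 19,488 (47.6%) |
| 1–56 days | 81,816 | 20,107 (24.6%) | 1,413 (1.7%) | 60,296 (73.7%) |

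These are shares of post-dose events whose onset day is missing. They are not shares of all AEs.

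**4. Effect on a table.** Section 1.3.2 gives 28 patients, and section 2.1 gives five cohorts of 3 to 6. Four cohorts hold at most 24, so all five are needed, and the only splits are (4, 6, 6, 6, 6) and (5, 5, 6, 6, 6). One lost subject moves a preferred-term incidence by 1/6 = 16.7, 1/5 = 20.0 or 1/4 = 25.0 percentage points. Because "Subjects with multiple events will be counted only once per SOC" and preferred term, this happens only if the subject has no other TEAE record of that term.

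**5. If imputation is not used.** The section 2.3.2 default then leaves the day missing, and the SAP does not say how such an event is classed.

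**The case against.** The strongest reply is that the effect is conditional at every step. Imputation is optional. The SAP does not say outright that imputed dates set the TEAE flag. The number of missing-day records may be zero. The percentages run from 24.6% to 83.6% depending on the window, and a narrower window would go higher. All of that stands, and none of these figures is an expected count of lost events. But the SAP offers no other way to class an event with an incomplete onset date, and it describes no other analysis that depends on an AE start date.

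The consequences are also bounded. There are no formal hypothesis tests, and DLTs have their own criteria in section 1.3.2. Deaths, end-of-treatment and end-of-study listings do not depend on TEAE status. Section 3.4.2 promises a listing of all AEs in which a wrong flag could be seen, and the imputation is to be documented. These points limit the harm, but none puts an event back into a table. The AE listings named in section 4.3 are TEAE listings only; the promised all-AE listing is not among them.

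The range of 17 to 25 points is not a strict bound. Section 1.4.4 replaces some dosed subjects and section 2.2 keeps every dosed subject in the FAS, so a cohort could exceed 6. Another could then hold 3 (33 points).

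**Conclusion.** The concern holds. Applied as written, section 2.3.3 together with section 3.4.2 classes new post-dose events in the month of first dose as pre-existing, and nothing else in the SAP corrects this. Conditions present at baseline that worsened after first dose still qualify, so the defect is confined to new AEs.

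Under the uniform assumption, about half of missing-day events with onset 1 to 28 days after first dose would be lost, and the share is higher for earlier onsets. The mechanism is certain from the text. Its effect on this trial's tables is unknown and could be nil. It should be fixed, because the stated rule gives a wrong answer in one direction and the correction is cheap.

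**What to change.** - In section 2.3.3, for AE start dates: if the known month and year (or the year alone, when day and month are missing) match those of first dose, impute the first-dose date, unless the AE stop date or other recorded data show onset before dosing. Otherwise keep the present rule. Say that this will be done, not that it may be. The concomitant-medication rule can stay.
- In section 3.4.2, define a TEAE as onset on or after first dose, using time where collected. Both changes are needed, because an onset imputed to the dosing date would fail a strict reading of *after*.
- As tidying, define the subject's study start date wherever it is still used, and add the all-AE listing to section 4.3.

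With the first two changes, all 40,908 post-dose pairs in the 1–28 day window are classed as TEAEs. The cost is a few sentences, a few lines of code and some over-counting. By symmetry with the count above, 21,420 / 40,908 = 52.4% of missing-day events that began 1 to 28 days before first dose fall in the first-dose month and would count as TEAEs, unless other data show the earlier onset. AEs dated on the first-dose day with no time recorded would also count. Both errors are in the conservative direction for safety.

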2.4. Statistical Methods

2.4.1. General Overview and Plan of Analysis

All data will be analyzed using Statistical Analysis System (SAS Version 9.4 or higher for Windows, SAS Institute, Cary, NC). Continuous variables will be summarized using number, mean, standard deviation, median, minimum, and maximum. Categorical variables will be summarized using frequencies and percentages.

2.4.2. Hypothesis Testing

No formal hypothesis tests are planned.

2.4.3. Modeling

Not Applicable in this study.

2.4.4. Multiplicity Issues/Multiple Comparisons

There is no planned Multiplicity Issues/Multiple Comparisons analysis for this study.

2.4.6. Interim Analysis

No formal interim analysis is planned. Appropriate safety listings and summary tables will be generated for Scientific Review Committee meetings and Development Safety Update Reports (DSURs).

2.4.7. Pharmacokinetic and Pharmacodynamic Analyses

Pharmacokinetic and Pharmacodynamic data will be summarized in a separate report.

3. Statistical Analysis

Data will be presented for clinical review and interpretation. Categorical variables will be summarized using frequency counts and percentages. Continuous variables will be summarized using descriptive statistics (n, mean, SD, median, minimum, and maximum). All listings will be presented for the FAS population except for PK and PD data.

3.1. Enrollment and Disposition of Subjects

Enrolled individuals are referred to as “subjects”. Subjects with advanced hematologic malignancies with FLT3 and/or Ras mutations, including acute myeloid leukemia (AML), myelodysplastic syndrome (MDS) or chronic myelomonocytic leukemia (CMML) will be included.

Major selection criteria are: age ≥ 18 years with confirmed diagnosis of FLT3+ and/or Ras+ higher-risk MDS/CMML (Phase 1 only), or relapsed or refractory AML with a FLT3 and/or Ras mutation. In the absence of rapidly-progressing disease, ≥ 3 weeks after prior cancer treatment for the disease under study, with the exception of hydroxyurea to control peripheral blast counts allowed during the first 2 cycles. Subjects must have recovered from all acute toxicities (\leq Grade 1), have adequate renal and hepatic function, and no known history of significant cardiac disease.

The analyses of subject disposition will be performed on the FAS population for all subjects and by dose cohort. The number of subjects treated, completed study and those who terminated early from the study, along with their reasons for early termination, will be presented.

3.2. Baseline Characteristics

3.2.1. Demographic

Summary statistics for demographic characteristics will be presented for subjects by dose cohort using the full analysis set (FAS) population. Tabulations will be performed for age, sex (male or female), ethnicity (Hispanic/Latino or other), and race (American Indian or Alaska Native, Black or African American, White, Asian, Native Hawaiian or Other Pacific Islander, Unknown, or other). Age will be calculated as the number of complete years between a subject’s date of birth and the date of screening visit. Demographic characteristics will be presented in listing for each subject.

